7. SAFETY

7.1 Potential risks & benefits to study participants

Confidential – This document and the information contained herein may not be reproduced, used or disclosed without written permission from Cumbria Partnership NHS Foundation Trust Page | 15

There is no anticipated personal safety risk associated with taking part in this study. If the research team learns of important new information that might affect the patient's desire to remain in the study, he or she will be told. Appropriate precautions are in place to ensure medical and personal information is kept safe through adhering to appropriate governance regulations. Any adverse events will be recorded, as outlined in sections below.

For the participants in the control group there is no direct benefit in taking part in this study. They will be cared for in exactly the same manner as they normally would. For participants in the Granulox intervention group, there may be benefits in terms of improved foot ulcer healing compared to normal standard care. Although there is initial evidence that this is indeed the case, this has not yet been proven and established through a prospective randomised trial, and this study is aimed to assess this. Participants cannot claim payments, reimbursement of expenses or any other benefits or incentives for taking part in this research.

7.2 Safety definitions

Adverse Event (AE)

Any untoward medical occurrence in a patient or other clinical investigation participant taking part in a trial of a medical device, which does not necessarily have to have a causal relationship with the device under investigation.

An AE can therefore be any unfavourable and unintended sign (including an abnormal laboratory finding), symptom or disease temporally associated with the use of the device, whether or not considered related to the device.

Serious Adverse Event

A serious adverse event is any untoward medical occurrence that:

- results in death
- is life-threatening
- requires inpatient hospitalisation or prolongation of existing hospitalisation
- results in persistent or significant disability/incapacity
- consists of a congenital anomaly or birth defect.

Other 'important medical events' may also be considered serious if they jeopardise the participant or require an intervention to prevent one of the above consequences.

NOTE: The term "life-threatening" in the definition of "serious" refers to an event in which the participant was at risk of death at the time of the event; it does not refer to an event which hypothetically might have caused death if it were more severe.

7.3 Procedures for recording adverse events

All AEs need to be reported to the sponsor/host Trust R&D within one working day of the investigator team becoming aware of them. For this purpose an AE report form is completed by the researcher and/or Chief Investigator

The relationship of each adverse event to the trial must be determined by the Chief Investigator, a medically qualified individual, according to the following definitions:

- Related: The adverse event follows a reasonable temporal sequence from swabbing. It cannot reasonably be attributed to any other cause.
- **Not Related**: The adverse event is probably produced by the participant's clinical state or by other modes of therapy administered to the participant.
- Severity grading: the Chief Investigator will also record if it concerns an AE or SAE.

This is recorded on the aforementioned AE reporting form. The forms are stored in the study site file.

Pseudo-anonymised copies of all adverse events forms will be shared with InFirst as soon as causality reporting has been performed and concluded.

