HAWS; Haemoglobin Application to Wounds Study, a single-centre, controlled, prospective randomized trial

Version 6, dd 10July 2018

Chief Investigator's Statement of Ownership and Content.

I, [name], confirm that this protocol is my work and is owned by me. The protocol conforms with standards outlined in the Declaration of Helsinki 1964.

Name (PRINT): [name]

Signature:

Date: LATH SEP. 2018

RESEARCH PROTOCOL SUMMARY

TITLE:	Haemoglobin Application to Wounds Study, a single-centre, controlled, prospective, randomized trial of Granulox
	haemoglobin spray for adjuvant treatment of foot ulcers
Short title:	HAWS; Haemoglobin Application to Wounds Study
IRAS number	227421
Device description	Granulox® Medical device. Class III, CE 0482
	Indications: Granulox® is a spray for use on chronic wounds. Granulox® is an innovative medical device for the proposed treatment of chronic wounds, such as venous leg ulcer, arterial leg ulcer, mixed leg ulcer, foot ulcers, secondary healing of surgical wounds and pressure sores. Granulox® can also be used on sloughy and infected wounds. Each canister contains 12 ml of spray, sufficient for 30 wound treatments.
Study design	Single-centre, controlled, prospective randomized trial
Primary objective	To determine the efficacy of the Granulox spray as an adjuvant therapy for foot ulcers at 3, 6, 9 and 12 weeks post-baseline - Healing rate (ulcer size; 12 weeks is endpoint for power calculation), as measured with surface area scoring grid
Secondary objectives	Clinical assessment at -2, 0, 3, 6, 9 and 12 weeks, and - PUSH ulcer size/grading score - Texas Univ grading score - Wound closure Safety of Granulox spray throughout trial duration, up to 12 weeks - Wound infection incidence; secondary interventions Patient-reported outcome measures at 0, 6 and 12 weeks - Patient mobility score (LifeSpace questionnaire) - Quality of life score (EQ-5D-5L and CWIQ) - Visual Analogue Score for pain associated with DFU Status of wound at week 18 - Healed, not healed, recurrence.
Patient population	A total of 60 participants, over the age of eighteen, with measurable foot ulcer, treated in clinic. Forty patients to have a DFU and further 20 patients to have nondiabetes related foot

	Indiana B. III in the second s
	ulcer. Participants must have the capacity to provide informed written consent and complete patient reported outcome measures.

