	 30 Patient will receive treatment as usual (TaU) 30 Patients will receive TaU plus adjuvant Granulox application twice weekly.
	Randomisation will be stratified for diabetes diagnosis (yes/no) and ulcer size, with cut-off PUSH score of 6 and above, or 5 or less. Patients will first go through a two week screening period; those patients with a healing rate of > 50% in 2 weeks will not be eligible for the intervention period.
Sponsor	Cumbria Partnership NHS Foundation Trust
Manufacturer & research grant provider	SASTOMED GMBH, https://granulox.de/en/sastomed contact: [name], EngelsConsult
	[name] [contact]; [contact] [contact]
Chief Investigator	[name] [name], GPwSI Research, [contact] or [name] [contact] Cumbria Partnership NHS Foundation Trust R&D Department, [name]
Co-investigators	[name] PhD, Science & Innovation Manager, [contact] or [name]; [contact] Cumbria Partnership NHS Foundation Trust R&D Department, [name]
	[name] Podiatry Lead Cumbria Partnership NHS Foundation Trust [name]
Organisation where research will take place	Cumbria Partnership NHS Foundation Trust Carleton Clinic R&D department [name]
	[contact]

Planned timeline	Recruitment start date (first patient, first visit) July 2017,
	Recruitment end date (last patient, first visit): 31 Jan 2019
	Trial end date: Apr 2019
Protocol version, date	Version 6, 10 July 2018

1.	Lay summary	6
2.	Introduction	6
3.	Investigational device	8
4.	Study hypothesis	9
4.1	Primary objective	9
4.2	Secondary objective	9
5.	Study protocol	9
5.1	Study design and timeline	9
5.2	Participant identification	10
5.3	Consent	11
5.4	Recruitment	11
5.5	Follow-up	12
5.6	Outcome measures	12
5.6.	1 Primary outcome measures	12
5.6.	2 Secondary outcome measures	12
6.	Subjects	13
6.1	Anticipated number of research subjects	13
6.1.	1 Randomisation	14
6.2	Eligibility criteria	14
6.2.	1 Inclusion criteria	14
6.2.	.2 Exclusion criteria	15
6.3	Early withdrawal of subjects	15
7.	Safety	15

7.1	Potential risks & benefits to study participants	15
7.2	Safety definitions	
7.3	Procedures for recording adverse events	
8.	Statistical consideration and data analysis plan	
8.1	Analysis of baseline characteristics	
8.2	Primary outcome statistics	
8.3	Secondary outcome statistics	.18
9. 1	Data handling and monitoring	.18
10.	Goverance of study	.19
10.1	Approvals	
10.2	Sponsor & Indemnity	19

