5.2 Participant identification and research setting

Participants will be recruited from podiatry clinics and all eligible patients will be invited to take part until the required numbers have been achieved. Identification will be by the podiatrists who are supporting the study. A screening form will be completed for potentially eligible patients to confirm that they indeed meet the trial criteria.

The podiatry team in West Cumbria will be supporting this study, and the study will take place in Whitehaven, Workington, Cockermouth and Wigton. All research activity and also treatment as usual (ie application of dressings) will take place in these clinic settings. Additional resource, paid for by the research grant for this study, means that there is sufficient capacity to treat study participants with the Granulox medical device. All podiatrists – 4 staff in total - will receive training on the use of the medical device by a representative of InFirst Healthcare.

To summarise, the podiatrists will:

- Identify potentially eligible patients and ask verbal consent for them beign approached about the study by a member of the R&D team
- Complete the incl/excl criteria part of the screening form
- Apart from treatment as usual activities (dressings, cleaning of wound, footwear advice), measure the wound size and complete the PUSH and Texas University score once a patient has consented to taking part (informed consent will be taken by members of R&D team, or one of the podiatrist so long as GCP training has been completed).

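### Section 7.3 ties a Related adverse event to swabbing, which is not a procedure of this trial, and its two causality categories leave a gap

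*Protocol*

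**What the plan says.** Section 7.3 makes a causality judgement compulsory for every adverse event: "The relationship of each adverse event to the trial must be determined by the Chief Investigator, a medically qualified individual". It supplies two definitions for the purpose. Related reads: "The adverse event follows a reasonable temporal sequence from swabbing. It cannot reasonably be attributed to any other cause". Not Related reads: "The adverse event is probably produced by the participant's clinical state or by other modes of therapy administered to the participant". No third category is offered. The judgement goes on the adverse event form, and pseudo-anonymised copies of all forms go to the company once causality has been concluded.

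The protocol summary gives the intervention as "TaU plus adjuvant Granulox application twice weekly" and lists among its secondary objectives "Safety of Granulox spray throughout trial duration, up to 12 weeks". Section 7.2 defines an adverse event independently of causality, covering any sign, "symptom or disease temporally associated with the use of the device, whether or not considered related to the device".

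**The concern.** The definition of Related rests on an exposure that participants do not receive under this protocol. The wording looks carried over from another study, though the document does not say so. Because section 7.3 tells the Chief Investigator to classify by these definitions, this is an operative rule and not background text.

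The second difficulty would survive correction of the word. The two categories use different thresholds: one asks whether another cause is reasonable, the other whether another cause is probable. Events between the two have no category.

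At stake is the attribution of events to Granulox. Safety is a stated objective, the trial is unblinded (section 6.1.1), the Chief Investigator alone judges causality, and section 9 says no steering committee will be convened. The protocol describes no second reading of causality that would catch a misapplied definition.

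**Working it through.** No arithmetic applies: the point does not depend on any rate, effect size or sample size. The check has three steps.

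**1. Is swabbing a trial procedure?** The summary and sections 5.4 and 6.1.1 describe a spray added to treatment as usual. Section 5.2 describes the podiatrists' work as "Apart from treatment as usual activities (dressings, cleaning of wound, footwear advice), measure the wound size", together with the wound scores; no swab is named. The measurement schedule (Table 3 in section 5.4) lists ulcer size, PUSH, Texas grading, healed status and questionnaires, again with no swab. In the text available, the word occurs only in the definition of Related. The appendix flowcharts are not shown, so they could not be checked.

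**2. Are the two categories exhaustive?** Three conditions matter:

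- S: the event follows the named exposure in a reasonable temporal sequence.
- R: another cause is reasonable.
- P: another cause is probable. P implies R.

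Related means S and not R. Not Related means P.

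| Event | Category, if S can be met (spray substituted) | Category, read literally (S never met) |
|---|---|---|
| No other reasonable cause, follows the exposure | Related | none |
| No other reasonable cause, does not follow the exposure | none | none |
| Other cause reasonable but not probable | none | none |
| Other cause probable | Not Related | Not Related |

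On the literal reading the Related category is empty, and even an event with no other reasonable explanation has no place. With the exposure word corrected, the third row still has none. That row is relevant here because participants have diabetes, peripheral arterial disease or another ulcer aetiology (section 6.2.1), so a competing explanation for an infection or a deterioration will often be reasonable.

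The direction of error follows. An event in the third row fails Related outright, because another cause is reasonable. If the assessor has to choose, the wording pushes towards Not Related or towards no entry.

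**3. What depends on the label?**

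- Section 7.2 counts an adverse event whatever its cause.
- Section 7.3 requires all adverse events to be reported to the sponsor within one working day, and all forms go to the company.
- The safety outcomes in the summary and section 5.6.2 are wound infection, secondary interventions and any other adverse events. None is restricted to related events.

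The label therefore affects the attribution recorded on the form and passed on with it. It does not affect which events are counted or reported.

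A further ambiguity is the target of the judgement. Section 7.3 asks about relationship to the trial, whereas section 7.2 speaks of relationship to the device. The two can give different answers, most plainly for control participants, who are in the trial but receive no spray.

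**The case against.** The strongest reply is that a medically qualified assessor would treat the word as a slip and read it as the study treatment. The context helps: section 7.2 refers to use of the device, and Not Related contrasts the exposure with the clinical state "or by other modes of therapy administered to the participant", which suggests that the exposure meant is itself a therapy. In practice, then, the related count need not be zero. This stands as a comment on likely practice. It remains a repair by guesswork, and it does nothing for the gap between the categories.

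A reader might infer that the trial's safety result would be wrong. The documents do not support that. The listed safety outcomes are all-cause, so the comparison between randomised arms is the same whatever label each event carries. No related-event count is named as an outcome, and no stopping rule or separate reporting route is made to depend on the label.

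A reader might also infer that most events could not be classified. That is unsupported too. Where the participant's condition is the probable cause, the event falls under Not Related. Only events with a reasonable but not probable alternative are stranded once the exposure word is corrected, and the protocol gives no figures from which to estimate their share.

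Finally, a narrow or a broad definition of Related is a legitimate choice. The defect is that the pair of definitions is incomplete, not that Related is strict.

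**Conclusion.** The definitions are wrong as written. Taken literally, no event can be Related; with the obvious substitution, events with a plausible but not probable alternative cause still have no category. The attribution of adverse events to Granulox is therefore unreliable and biased towards too few related events.

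Severity is minor to moderate. One field on the adverse event form is affected, together with the causality information the company receives. All-cause comparisons between arms and the reporting of all events to the sponsor are intact.

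The conclusion rests on swabbing being absent from the parts of the protocol not shown. The direction of bias assumes that events meeting neither definition are not recorded as Related. The number of events involved cannot be estimated from the protocol.

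**What to change.** In section 7.3 and on the adverse event form:

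- Replace swabbing with application of Granulox or another trial procedure.
- State whether the judgement is relatedness to the device or to the trial, and use the same term in sections 7.2 and 7.3.
- Make the categories exhaustive. One way is to define Related as a reasonable possibility that the device or a trial procedure caused or contributed to the event, and Not Related as no reasonable possibility. Another is to add a possibly related level.
- Re-read the causality field on any forms already completed under this same wording. Recruitment was planned from mid-2017 and this version is dated July 2018, so such forms may exist. Whether earlier protocol versions used the same definition cannot be seen from the document.

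The cost is a short protocol and form amendment and a re-read of existing forms. A few more events may be labelled related.

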8. STATISTICAL CONSIDERATION AND DATA ANALYSIS PLAN

8.1 Analysis of baseline characteristics

To determine the demographics and characteristics of the patients in the two arms the following data will be collated:

- Age
- Gender
- BMI
- Smoking status
- Significant comorbidities, including peripheral arterial disease, heart failure, pretibial oedema.
- Aetiology and location of wound
- Presence of diabetes, and if so length of having condition
- Neuropathy
- Offloading of the foot ulcer
- Ankle-Brachial Index value (measured within last 3 months)
- Wound infection or not (or infected at any stage of participation)

Any differences in distribution will be established with Chi-squared test or ANOVA as indicated.

8.2 Primary outcome statistics

The primary objective for this trial is the healing rate of the foot ulcers, as assessed by tracing the wound using a Convatec measuring grid, or an equivalent measuring grid tool.

Confidential – This document and the information contained herein may not be reproduced, used or disclosed without written permission from Cumbria Partnership NHS Foundation Trust Page | 17

The average difference between time points will be calculated per group, 12 weeks being the primary endpoint but weeks 3, 6 and 9 will also be analysed. To compare the groups, the Mann-Whitney U-test will be applied.

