To further illustrate the point concerning the impact of foot ulcers: the healing rate of DFUs is poor; on average, 24% of wounds have healed by week 12 of treatment, and only 31% at 20 weeks of treatment (Margolis, 1999). A cohort study involving 31 diabetic patients determined that the average healing time for neuropathic DFUs is 78 days whereas this increases to 133 days for patients with additional peripheral vascular disease (Zimny et al, 2002). Further analysis has shown that the size of the ulcer negatively correlates to the healing rate, whereas a patient's age, sex, or type of diabetes is not associated with a change in healing rate outcome (Oyibo, 2001). DFU healing progress at 4 weeks of treatment is a predictor of the likelihood that the wound will be healed by 12 weeks of treatment. If the wound has not healed by at least 50% after 4 weeks, the likelihood that the DFU will be completely healed by 12 weeks is reduced to circa 10% (Sheehan, 2003). Taken together, there is a major group of patients with DFU -those with larger ulcers, and co-morbidities, responding poorly to standard treatment in the first 4 weeks – that is at risk of ending up with long-term wounds taking over 3 months to heal, if at all.

Oxygen is an essential component of the wound healing process (Hunt et al, 1969). Poor circulation due to diabetic angiopathy impairs the healing process and limits the degree of required growth factor release and angiogenesis (Falanga, 2005; Mathieu et al, 2006). Increasing oxygen levels can be achieved in various ways, including hyperbaric chamber treatment (Faglia, 1996). However, this method is costly, cumbersome and logistically challenging. A novel haemoglobin spray that is designed to enhance wound healing, including non-diabetic foot ulcers and DFUs, by enriching the wound area with oxygen using porcine haemoglobin is now available in the UK. The product is called Granulox and it marketed by InFirst Healthcare Ltd. The mode of action is the application of porcine haemoglobin onto a wound to facilitate increase oxygen levels through diffusion into the wound area (Arenberger et al, 2011; Norris, 2014; Hunt & Elg, 2016). Hunt & Elg, in a study with retrospective analysis of standard care DFUs and prospective assessment of Granulox adjunct therapy DFUs, have shown that the healing rate for chronic wounds is much accelerated with haemoglobin treatment. Figure 1 summarises their data.

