6. SUBJECTS

6.1 Anticipated number of research subjects

There is pilot data to base a *priori* sample size calculation on, but this concerns a single retrospective study (Hunt and Elg, 2016). In their study, they observed 37% (control) and 89% (Granulox) wound size change versus baseline measurement at 12 weeks. This would mean that 14 patients (7 in each arm) would be sufficient to have the trial powered to 80%. For this present trial, a more conservative approach is taken, see Table 4. The earlier published average healing rate of 25% is used as the anticipated minimum healing rate (Margolis, 1999). Since some patients may require surgical intervention or may withdraw, a hypothetical 20% dropout rate is calculated into the sample size (actual attrition rate is a study objective). A theoretical 1:1 allocation to the control and Granulox intervention group respectively will be applied. However, because the PUSH score is not known beforehand this may not be achieved if more patients are recruited into one of the two PUSH cohorts. Diabetic foot ulcers (DFUs) and other foot ulcers will be randomised from separate randomisation lists.

The primary outcome, average percentage decrease in ulcer size between baseline and 12 week follow-up is used for sample size calculation. Power calculations for sample size, 80% power and 5% significance, based on two-sided Mann-Whitney U-test. A priori power calculations using GPower 3.1 software, result in the following sample size summarized in Table 4. This is based on the DFU study by Hunt and Elg. A further 20 patients with non-diabetic foot ulcers will be recruited to pilot what impact Granulox has on those types of wounds.

Table 4, Sample size calculation

	Median change in DFU ulcer size at 12 weeks (presume decrease for both arms, ie one-tailed approach)	Standard Deviation
Arm A (hypothetical)	52%	30%
Arm B (hypothetical)	25%	30%
	Power beta of 80%, Alpha p-value of Sample size required without any dro	

Sample size with 20% attrition rate included: 40

Total of 40 DFU patients:

- 20 Patients to receive treatment as usual (TaU)
- 20 Patient to receive TaU plus Granulox spray

Plus 20 non-DFU foot ulcers:

- 10 Patients to receive treatment as usual (TaU)
- 10 Patient to receive TaU plus Granulox spray

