6.1.1 Randomisation

Following written consent at -2 weeks, participants will be observed for two weeks to establish healing rate. At the end of two weeks, patients are only eligible for the intervention phase if their wound has healed <50% in the preceding two weeks. At this point, week 0, participants are allocated at random to the control or Granulox intervention group, using a randomised sequence from the freeware randomisation programme, see https://www.randomizer.org/. The randomisation is stratified for ulcer size, with PUSH score of 5 or less, and 6 or above as the cut-off. This size has been determined as the average size of a presenting foot ulcer previously (Zimny et al, 2002).

Sequential envelopes with each next randomisation allocation will be used to achieve concealment and these will be kept in the research department. The researcher will then inform the regular healthcare professional for the participant in question, and the participant themselves, which treatment they've been allocated to. The researcher will dispatch a Granulox canister to the clinic where the participant will be seen. At this stage the twice weekly treatment (though three applications per week would be allowed if dressing change is more than twice a week) will commence.

As the study involves administration of a spray it is not possible to achieve blinding for the participants nor the researchers – it is recognised that this increases the risk of bias.

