APPENDIX 1. TOOLS AND ASSESSMENTS

This appendix contains:

- The PUSH tool that will be used to assess each leg ulcer at -2, 0, 3, 6, 9 and 12 weeks (from Stotts et al, 2001)
- Texas University ulcer grading score at -2, 0, 3, 6, 9 and 12 weeks (from Armstrong et al, 1998)
- The mobility life space questionnaire that will be completed for each participant to confirm limited mobility at 0, 6, and 12 weeks (from Stalvey et al 1999)
- The EQ-5D-5L Questionnaire used to score generic quality of life for each participant at 0, 6, and 12 weeks
- The Cardiff Wound Impact Questionnaire used to score wound-related quality of life for each participant at 0, 6, and 12 weeks (from Price & Harding, 2004) see separate document
- Visual analogue pain scale at -2, 0, 3, 6, 9 and 12 weeks

Pressure Ulcer Scale for Healing (PUSH) **PUSH Tool 3.0**

Patient Name	Patient ID#
Ulcer Location	Date

Directions:

Observe and measure the pressure ulcer. Categorize the ulcer with respect to surface area, exudate, and type of wound tissue. Record a sub-score for each of these ulcer characteristics. Add the sub-scores to obtain the total score. A comparison of total scores measured over time provides an indication of the improvement or deterioration in pressure ulcer healing.

Sub-sco	5	4	3	2	1	0	LENGTH
	2.1 – 3.0	1.1 – 2.0	0.7 – 1.0	0.3 - 0.6	< 0.3	0	X WIDTH
	10	9	8	7	6		
	> 24.0	12.1 – 24.0	8.1 – 12.0	4.1 – 8.0	3.1 – 4.0		(in cm²)
Sub-sco			3	2	1	0	EXUDATE
			Heavy	Moderate	Light	None	AMOUNT
Sub-sco		4	3	2	1	0	TISSUE
		Necrotic Tissue	Slough	Granulation Tissue	Epithelial Tissue	Closed	TYPE
TOTAL SC							

Texas University grading score

University of Texas Diabetic Wound Classification Diabetes Care 1998; 21: 855-859

Stage	Grade				
	0	1	2	3	
A	Pre or post lesion – intact	Superficial wound	Penetrating to tendon or capsule	Penetrating to bone or joint	
В	+Infection	+Infection	+Infection	+Infection	
С	+Ischaemia	+Ischaemia	+lschaemia	+lschaemia	
D	+Infection and ischaemia	+Infection and ischaemia	+Infection and ischaemia	+Infection and ischaemia	

Life Space Questionnaire

Interviewer: "I am interested in all the places that you have been within the last 2 weeks"

1	Dender all the second of the s				
1.	During the past 2 weeks have you been to other rooms of your home besides the rowhere you sleep?	om			
	1 =Yes 2=No				
2.	During the past 2 weeks have you been to an area immediately outside your home, so your porch, patio, garage?	such as			
	1 =Yes 2=No	1			

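### Randomisation is stratified by diabetes and PUSH size band, but the primary Mann-Whitney test uses neither, which costs some power if the strata are prognostic

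*Protocol*

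**What the plan says.** **Randomisation.** The protocol summary states: "Randomisation will be stratified for diabetes diagnosis (yes/no) and ulcer size, with cut-off PUSH score of 6 and above, or 5 or less". Section 6.1 puts the diabetes factor into practice: "Diabetic foot ulcers (DFUs) and other foot ulcers will be randomised from separate randomisation lists". Section 6.1.1 mentions only the size factor: "The randomisation is stratified for ulcer size, with PUSH score of 5 or less, and 6 or above as the cut-off". It adds that this cut-off is the average size at presentation, citing an earlier cohort study. No block size is given.

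**Prognosis.** Section 2 reports from a cited analysis that "the size of the ulcer negatively correlates to the healing rate". It gives no strength for the relation and makes no comparable statement about diabetes versus no diabetes.

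**Primary analysis.** Section 6.1 takes percentage decrease in ulcer size from baseline to 12 weeks as the primary outcome. Section 8.2 says of the comparison: "To compare the groups, the Mann-Whitney U-test will be applied". No strata or covariates are named. The only covariate-adjusted analysis is the Cox model in section 8.3, under secondary outcomes.

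**PUSH.** The tool in Appendix 1 scores area, exudate and tissue type, and instructs: "Add the sub-scores to obtain the total score".

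**The concern.** Stratified allocation makes the arms alike on the chosen factors. A test that ignores those factors still treats the differences between strata as random noise. Two things follow if the factors predict outcome:

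- the test has less power than one that compares patients within strata;
- where allocation is forced to balance within strata, the test's assumed variance is too large, so p-values are too big on average.

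The test is named outright in the protocol, so this is a stated choice and not a detail left open. It matters more because there is little power to spare, as the first step of the working shows.

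A second, smaller matter concerns the size factor. If the cut-off refers to the PUSH total, the band mixes area with exudate and tissue type and is only a rough measure of size.

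**Working it through.** **1. The plan's own sample size.** Inputs from section 6.1 and Table 4: 52% versus 25%, SD 30%, 80% power, 5% significance, 20% attrition. The standardised effect is 27/30 = 0.9. With n per arm = 2(z_alpha + z_beta)²/0.9²:

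- one-sided: 2(1.645 + 0.842)²/0.81 = 15.3, so 16 per arm, 32 in total, and 32/0.8 = 40. This matches the stated 40;
- two-sided Mann-Whitney (t-based, efficiency 3/π): 22 per arm, 44/0.8 = 55. This does not match.

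The text of section 6.1 says "Power calculations for sample size, 80% power and 5% significance, based on two-sided Mann-Whitney U-test", while Table 4 says one-tailed. With 16 evaluable per arm, two-sided Mann-Whitney power is about 67%. The strata play no part in this calculation.

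**2. Type I error of the plain test under exact balance within strata.** If the strata explain a share R² of the outcome variance, the rank difference between arms has about (1 − R²) of the variance that the test assumes. The true level is therefore about 2[1 − Φ(1.96/√(1 − R²))]:

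- R² = 0.10: 1.96/√0.90 = 2.066, giving 3.9%;
- R² = 0.20: 1.96/√0.80 = 2.191, giving 2.8%.

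**3. Power by simulation.** From the protocol: 60 randomised (40 DFU, 20 other), effect 27 points, total SD 30, 20% drop-out, two-sided 5%. Assumed: normal outcomes, an even size split (strata of 20/20/10/10), a size shift twice the diabetes shift, blocks of four within strata, random drop-out, and R² varied. There were 20,000 null runs and 8,000 runs with the effect. Rank ANCOVA here adjusts for strata only.

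| Set | R² | Plain: type I error | Power: plain | van Elteren | Rank ANCOVA |
|---|---|---|---|---|---|
| All, about 48 evaluable | 0 | 4.9% | 84.1% | 80.6% | 83.5% |
| | 0.05 | 4.6% | 84.3% | 82.6% | 85.2% |
| | 0.10 | 4.1% | 84.7% | 85.2% | 87.0% |
| | 0.20 | 3.2% | 84.8% | 88.2% | 90.0% |
| | 0.30 | 2.4% | 85.6% | 92.1% | 93.1% |
| DFU, about 32 evaluable | 0 | 4.7% | 66.8% | 65.4% | 67.1% |
| | 0.10 | 3.9% | 65.8% | 68.9% | 70.5% |
| | 0.20 | 3.2% | 66.5% | 73.9% | 75.3% |
| | 0.30 | 2.4% | 66.3% | 79.0% | 80.1% |

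Gains of rank ANCOVA over the plain test at R² of 0.10 and 0.20:

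- all patients: 87.0 − 84.7 = 2.3 and 90.0 − 84.8 = 5.2 points;
- DFU only: 70.5 − 65.8 = 4.7 and 75.3 − 66.5 = 8.8 points.

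Both adjusted tests hold close to 5% type I error. A second run with exactly balanced evaluable strata agreed with these gains to within about a point, with plain type I error of 2.7-3.7%. With simple, unblocked randomisation the plain test stays at about 5% and only power is lost (for example 82.8% against 88.3% at R² = 0.20, all patients).

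**4. What the PUSH band measures.** In Appendix 1 an open ulcer scores 1-10 for area, 0-3 for exudate and 1-4 for tissue (tissue 0 means closed). That makes 10 × 4 × 4 = 160 combinations, of which 20 total 5 or less.

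- The largest area sub-score among those 20 is 5 − 0 − 1 = 4, that is 1.1-2.0 cm2.
- With granulation tissue (2) and light exudate (1) the limit is sub-score 2, or 0.6 cm2.
- A 1.5 cm2 ulcer with epithelial tissue and no exudate totals 4 + 0 + 1 = 5 (lower band). A 0.2 cm2 ulcer with necrotic tissue and light exudate totals 1 + 1 + 4 = 6 (upper band).

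On the area sub-score alone, 5 or less would mean up to 3.0 cm2. On the total, the boundary corresponds to no single area, so it cannot be an average presenting size.

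**The case against.** The strongest reply is that the benefit is conditional and may be small, and much of that stands.

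- **Prognostic strength is assumed.** Section 2 supports size only, for healing rate, without a figure. It is tempting to infer that both factors were chosen because healing depends on them, but no effect of diabetes on the outcome is documented.
- **Weak strata leave little to gain.** At R² of 0.05 or less, van Elteren is worse than the plain test in the 48-patient set, and rank ANCOVA is about level with it.
- **A lopsided size band explains less.** With an assumed 10% of patients in the low band, a 1 SD size shift, no diabetes effect and a treatment effect of 0.7 SD, the plain and van Elteren tests both have about 60% power.
- **Large losses need chosen inputs.** A gap such as 46% versus 62% appears with an effect of 0.7 SD and 1 SD shifts on both factors added to the within-stratum SD. The protocol's own effect is 0.9 SD on an SD of 30.
- **A reader might infer a generally invalid p-value.** The level departs from 5% only if allocation is balanced within strata. The 20/20 and 10/10 targets suggest balance, but no blocking is stated and section 6.1 concedes that 1:1 may not be reached. Any departure is towards caution.
- **A reader might infer that nearly every ulcer lands in the upper band.** The 20 of 160 figure counts score combinations, not patients, and the protocol gives no size distribution.
- **Pooling of diabetic and other ulcers is not certain.** Section 8.2 does not define the analysis set, and section 6.1 powers only the DFU patients. In a DFU-only analysis the diabetes factor drops out.

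What survives is that the primary test ignores factors built into the randomisation, at least one of which the protocol itself links to healing, and that adjusting for them has almost no downside.

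**Conclusion.** The mismatch between stratified randomisation and an unstratified primary test is real, and its consequence is moderate and conditional. If the strata explain 10-20% of outcome variance (an assumption), a stratum-adjusted rank analysis gains about 2 to 5 power points in about 48 evaluable patients, or about 5 to 9 in about 32 DFU patients, at the protocol's planning effect. If the lists are also balanced within strata, the plain test runs at roughly 3-4% instead of 5%. This is lost efficiency; the documents do not support a claim of false-positive inflation or of an invalid trial. With no stratum effect, rank ANCOVA costs under one point, and van Elteren about 1 to 3.5.

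Separately, and without any assumption about effects, the PUSH total is a rough proxy for size, and the statement in section 6.1.1 about average presenting size does not fit it.

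**What to change.** **Section 8.2.** Make the primary comparison a rank analysis of covariance on 12-week percentage change in ulcer area, with treatment arm and the strata as randomised: diabetes and size band, or size band only if the analysis set is the DFU patients. Include baseline grid area (cm2) as a covariate there, or in a supporting analysis. The van Elteren test over the same strata is an acceptable alternative, with baseline area then handled in the supporting analysis.

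**Section 6.1.1.** State whether the cut-off refers to the PUSH total or to the length × width sub-score, and correct the sentence about average presenting size. Do not redefine the band for the remaining patients: that would mix two definitions in one factor. The measured baseline area deals with size.

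**Cost.** One sentence in each section, recorded before any comparison by arm because the trial is unblinded. No extra data are needed, since grid area and PUSH are already collected at week 0, and the sample size is unchanged.
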